3.0 Research Methods

3.1 Subject Selection: Eighty four boys and girls, between 6 to 20 years of age, diagnosed with IgE-mediated milk allergy, will be recruited for the study. Participants will be recruited from the allergy clinic at the Montreal Children's Hospital, Hopital Ste Justine, and the Centre de santé et de services sociaux de Chicoutimi.

Inclusion criteria: Children 6 years and older who satisfy **all** the following criteria will be included:

a. A **history** suggestive of IgE-mediated allergy to milk. An IgE-mediated reaction to a specific food is defined as a minimum of 2 mild symptoms and/or 1 moderate and/or 1 severe symptom that began within 1-20 minutes after ingestion or contact. Mild IgE-mediated symptoms include: pruritus, urticaria, flushing, or rhinoconjunctivitis. Moderate symptoms include angioedema (of face or lips), throat tightness, gastrointestinal complaints (vomiting, cramping, pain and/or diarrhea), or airway involvement (cough, nasal blockage, mucous); severe symptoms include bronchospasm, wheezing, hypoxia, cyanosis, low blood pressure, or circulatory collapse (shock) (appendix A ,table 1) (61).

b. The presence of **at least one** of the following confirmatory tests:

- (a) Positive skin prick test to milk (weal diameter 3 mm larger than that of the normal saline control). The allergen used will be commercially available milk extracts (Omega Labs, Montreal, QC). Skin tests will traced in ink, tape transferred to paper and wheal diameter measured by computer assisted planometry.
- (b) Detection of serum specific IgE (>0.35 kU/L) to milk or any of its proteins, measured by fluorescence enzyme immunoassay (Immunocap, Phadia, Uppsala, Sweden). The range for Immuncap is 0.35 – 100 and changes over time can be monitored effectively.

Following explanation of all facets of the protocol, informed consent and assent forms will be signed by the parents or legal guardian and subject, if applicable (Appendix B).

Exclusion criteria.

1. Patients with uncontrolled asthma or other uncontrolled respiratory diseases .
2. Malignancies, autoimmune diseases and/or severe primary or secondary immune deficiencies.
3. Patients receiving immunosuppressive therapy.
4. Patients receiving β -blockers (including topical formulations).
5. Associated diseases contraindicating the use of epinephrine: cardiovascular disease or severe hypertension.

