3.3.2 Escalation phase

Once subjects reached the dose of 2.5 ml undiluted milk, they will be instructed to repeat this dose at home daily for 2 weeks. They will then come to the research unit, and will be given an increased dose of 4 ml. This will be continued for one week, with incremental increases given weekly for 16 weeks, until a dose of 200 ml is reached. If a patient is unable to increase past a particular dose they will continue on this dose until the end of the 16 week acceleration phase.

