3.3.3 Maintenance phase

Patients who reach the maintenance dose of 200 ml will be instructed to continue and consume 200 ml of milk daily for 1 month. They will then undergo an oral challenge (see above), with the maximum dose of 300ml.

If this 300 ml dose is tolerated, they will be permitted to consume dairy products without restrictions and attend regular follow up visits for 12 months. It will be recommended to consume dairy at least twice weekly, if not more, to maintain the desensitization.

Subjects who tolerate less than the 200 ml upper dose will be instructed to continue their maximum tolerated dose for the 12 month follow-up period, at which time another blinded milk challenge will be performed to determine if their tolerance increased.

3.3.4 Long Term Follow-up: to assess the persistence of milk desensitization from clinical, cellular and molecular perspectives, participants will be asked to return to the research center once a year for five years following the end of the Maintenance Phase. At these visits, participants will be asked about their dairy consumption, any reactions they may have experienced in the interval between the last visit and changes in their quality of life (as assessed by questionnaire). Participants will also have the following analyses done: SPT, salivary IgA, serum milk-specific IgE, IgA and IgG4 concentrations, Glycosylation state, Vitamin D levels, and B and T cell regulatory cell phenotyping. Participants will be reminded of the importance of continuing the consumption of dairy products in the maintenance of desensitization. Participants who have completed the study will be asked to reconsent to the extension. Given that these participants may not have scheduled visits to the hospital, to lessen their inconvenience, a delegated member of the study team might make a home visit in order to obtain informed consent

3.3.4 Control Subjects: Subjects randomized to no treatment will be followed every 3-6 months as is standard in our clinic for milk allergy. They will have skin testing and blood testing as on routine follow-ups, but they will be required to fill out symptoms diaries. At the end of the study period, oral desensitization will be offered to the control patients who had not spontaneously achieved tolerance.

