Withdrawal from therapy: Subjects will be carefully monitored during the in hospital rush therapy phase, as well as during the home OIT phase. Instructions for treatment of reactions will be provided as above. Patients who are enrolled will be informed that in previously published studies, minor allergic reactions are common in these protocols (mild itching, abdominal discomfort) but resolve with increased time on therapy. Subjects will be withdrawn if they cannot tolerate the low dose, rush desensitization phase, if they have more than 2 or more moderate or severe reactions during the home (maintenance) OIT phase, if they experience a rare or unforeseen complication such as severe flares of eczema or chronic gastrointestinal symptoms (e.g. development of eosinophilic esophagitis) and if the parents or subjects wish to voluntarily terminate therapy.

3.3.6 : Variables measured. The following variables will be measured in each patient:

A. The primary outcome measure will be the presence of desensitization defined by the ability to tolerate 200 ml of milk 1 year after the start of the trial. This is a qualitative variable with three categories: total desensitization (200 mL of cow's milk); partial desensitization (20–200 mL); and failed desensitization (<20 mL milk). Only patients presenting total desensitization were regarded as being successfully desensitized.

B. Secondary outcome measures will be:

1. Number and severity of adverse reactions occurring after oral exposure to milk during the desensitization and follow-up phases.
2. Minimum dose of milk that triggered symptoms during the desensitization protocols or challenge tests.
3. Days until desensitization was achieved.
4. Indices of desensitization :
 - a. Change in skin prick test weal size, comparing tape transferred, cpoputor measured diameters and areas of the skin tests to milk extract.
 - b. Levels of sIgE, sIgA and sIgG4 before desensitization, during follow-up and at the end of the study.
 - c. T and B reg before desensitization, during follow-up and at the end of the study.

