Appendix A Scale for grading reaction Severity

Score	Symptom
Mild	Pruritus, Urticaria, Flushing, Rhinocconjunctivitis
Moderate	Angioedema, Throat tightness, Gastrointestinal complaints (cramping, pain, vomiting, diarrhea) Respiratory symptoms (Cough, Mucous production)
Severe	Wheeze, Respiratory Distress Hypoxia, Cyanosis, Hypotension Circulatory collapse (Shock)

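### The withdrawal rule for allergic reactions states two incompatible counts, so a participant with exactly two moderate or severe home reactions is both withdrawn and kept on treatment

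*Combined protocol and SAP*

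**What the plan says.** The rule stands in the Withdrawal from therapy paragraph of section 3.3.5. Among the grounds for withdrawal, it lists subjects "if they have more than 2 or more moderate or severe reactions during the home (maintenance) OIT phase". The paragraph opens by naming two settings: "Subjects will be carefully monitored during the in hospital rush therapy phase, as well as during the home OIT phase".

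Home dosing begins in section 3.3.2. Once participants reach 2.5 ml of undiluted milk, "they will be instructed to repeat this dose at home daily for 2 weeks", and weekly increases follow. Those who cannot increase stay at their dose "until the end of the 16 week acceleration phase". Maintenance has its own section, 3.3.3, which begins with "Patients who reach the maintenance dose of 200 ml". Appendix B puts 200 ml at weeks 17 to 52.

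On severity, Appendix A has Mild, Moderate and Severe levels and lists under Moderate "Gastrointestinal complaints (cramping, pain, vomiting, diarrhea". Section 3.1 grades the same kind of complaint as moderate: "gastrointestinal complaints (vomiting, cramping, pain and/or diarrhea". The withdrawal paragraph also tells families that "minor allergic reactions are common in these protocols (mild itching, abdominal discomfort".

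Section 4.0 gives a sample size of 42 per arm, t-tests, descriptive statistics and regression. It names no analysis set and no handling of participants who are withdrawn. Section 3.3.6 counts only total desensitization as success.

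**The concern.** A stopping rule for individual participants has to give the same answer to everyone who applies it. This one does not. *More than 2* means three or more, and *2 or more* includes two. It looks like a drafting slip, but the text does not show which half is the slip, so a site cannot repair it by reading. Three recruiting sites are named in section 3.1, and they could apply it differently. The decision at stake is whether a child with IgE-mediated milk allergy goes on taking the allergen at home after two moderate or severe reactions.

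The phase wording adds a smaller uncertainty. If only maintenance counts, reactions at home during up-dosing never enter the count.

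There is also a conditional effect on the results. Withdrawals for reactions, or for not tolerating the rush phase, can arise only in the OIT arm. If those participants were left out of the 1-year outcome, OIT success could be overstated.

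**Working it through.** **1. Count.** Let X be the number of qualifying reactions in one participant.

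| X | At least 2 | At least 3 |
|---|---|---|
| 0 or 1 | stays | stays |
| 2 | withdrawn | stays |
| 3 or more | withdrawn | withdrawn |

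The readings differ in one case only, X = 2.

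**2. How many participants that could be.** The documents give no reaction rate, so this is illustration on assumed inputs. With X Poisson with mean m, P(X = 2) = e^(−m) m²/2, and the expected number is 42 times that.

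| Assumed m | P(X = 2) | Of 42 |
|---|---|---|
| 0.1 | 0.0045 | 0.2 |
| 0.25 | 0.0243 | 1.0 |
| 0.5 | 0.0758 | 3.2 |
| 1 | 0.1839 | 7.7 |

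The Poisson maximum is 0.2707 at m = 2, or 11.4 of 42. With a more dispersed count (negative binomial, k = 1) the maximum is 4/27 = 0.1481, or 6.2 of 42. These maxima belong to the assumed distributions and are not bounds on this trial.

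**3. Phase.** Appendix B first lists 200 ml at week 17, so on schedule the narrow reading leaves out about 16 weeks. The figure is approximate: section 3.3.2 gives two weeks at 2.5 ml before 4 ml, while Appendix B lists 4 ml at week 2. The share of treatment depends on how long maintenance is taken to last:

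- One month at 200 ml (first step in section 3.3.3): 16/(16 + 4) = 80%.
- Appendix B's 52 weeks: 16/52 = 31%.
- One month plus the 12-month follow-up in section 3.3.3: 16/(16 + 4 + 52) = 16/72 = 22%.

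**4. Effect on the reported success rate.** Suppose w of the 42 OIT participants are withdrawn, s of the other 42 − w succeed, and x of the withdrawn would count as successes. Leaving the withdrawn out changes the rate by

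s/(42 − w) − (s + x)/42 = (w/42) × [s/(42 − w) − x/w], for w above 0.

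The values of w, s and x are assumed.

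| w | s | x | Withdrawn left out | All randomised |
|---|---|---|---|---|
| 2 | 28 | 0 | 28/40 = 70.0% | 28/42 = 66.7% |
| 4 | 27 | 0 | 27/38 = 71.1% | 27/42 = 64.3% |
| 8 | 24 | 0 | 24/34 = 70.6% | 24/42 = 57.1% |
| 8 | 24 | 6 | 24/34 = 70.6% | 30/42 = 71.4% |

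With no withdrawals there is no difference. The last row shows that the direction can reverse.

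**5. Effect on the comparison of arms.** With w = 8 and x = 0, two-sided Fisher exact tests against assumed control successes give:

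| Controls | 24/42 | 24/34 |
|---|---|---|
| 2/42 | 1.8 × 10⁻⁷ | 7.5 × 10⁻¹⁰ |
| 4/42 | 5.6 × 10⁻⁶ | 3.8 × 10⁻⁸ |

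On these inputs the conclusion is the same either way.

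**The case against.** The best case on the other side is that only the count is truly contradictory. Most of that case stands.

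- **Phase.** A reader might infer that this contradiction equals the count. It does not. The paragraph names only the hospital rush phase and the home phase, which favours counting all home dosing. What remains is a bracketed word that elsewhere names a separate, later phase. That is an ambiguity to clear up.
- **Grading.** A reader might infer that moderate is undefined, because the paragraph calls abdominal discomfort minor. The documents do not support that. Appendix A is the only severity scale, section 3.1 refers to it, and the rule uses its terms. The remark about minor reactions describes what families are told about published studies and does not grade anything. Only a cross-reference is missing.
- **Share of treatment.** A reader might take 31% as the document's figure. It holds only if Appendix B's weeks 17 to 52 are the maintenance phase. Section 3.3.3 describes one month at 200 ml, a challenge, and then unrestricted dairy for those who pass, so only a range is fair.
- **Exclusion.** A reader might infer that withdrawn participants will be dropped from the analysis. The plan does not say so, and the success definition in section 3.3.6 suggests they are not successes. The denominator is simply not stated.
- **Frequency.** Section 1.6 reports many reactions in earlier trials, mostly mild to moderate, but does not separate those that would qualify. Section 3.3 describes the source protocol as having few side effects. How often exactly two would occur is unknown.

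Appendices D and E, cited in section 3.3.5 for the diary and the reaction instructions, are not in the public text and could not be checked.

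None of this touches the count.

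**Conclusion.** The withdrawal rule is wrong as written on the count and must be corrected. That conclusion rests on the wording alone and needs no assumed rate: a safety threshold for children that gives opposite answers at exactly two reactions cannot be applied consistently. Confidence is high on this part.

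The phase is a lesser ambiguity, affecting about 16 weeks of up-dosing on schedule, or 22% to 80% of treatment. Grading needs only a cross-reference.

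The gap in section 4.0 is an omission, and its consequence is conditional. In the illustrations, leaving withdrawn participants out moves the OIT success rate by between −0.8 and +13.4 percentage points. The size of the reported benefit is at stake. On the inputs shown, the finding of a difference between arms is not. A claim that the trial's conclusion would be overturned is not supported.

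**What to change.** 1. Reconcile the withdrawal paragraph in section 3.3.5 with sections 3.3.2 and 3.3.3 and Appendix B, so that the rule gives one reaction count and one clearly bounded phase. Cite Appendix A as the grading basis. The sponsor decides which count and phase apply; none is proposed here.

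2. If handling is added to section 4.0.B, cover everyone in both arms. For example: *All randomised participants are analysed in their assigned arm. Withdrawal from therapy is not withdrawal from follow-up. Any participant in either arm without a 1-year result is counted as not totally desensitized in the primary comparison. A sensitivity analysis varies the outcomes of these participants in both arms. Any analysis of completers only is supportive.* Another rule would serve if it applies to both arms and is fixed before the data are seen. This text does not ask for a challenge after withdrawal, which stays with the investigator's safety judgement.

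The first change costs a few words. The second costs a short paragraph, some effort to keep withdrawn participants in follow-up, and possibly a less favourable reported success rate.

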2.0 Hypothesis: Children who are allergic to milk can be treated via a supervised program of oral immunotherapy (OIT). Successful treatment will be indicated by the ability to ingest dairy products daily with no adverse symptoms. This will be accompanied by a decrease in specific IgE to milk, an increase in IgA and IgG4 blocking antibodies and by increases in milk-specific Regulatory T-cells (Treg) and Regulatory B-cells (Breg).

2.1 Specific Objectives: 1) To determine the efficacy of Oral immunotherapy (OIT) treatment for children with IgE mediated cow's milk allergy (CMA)

2) To determine the safety of OIT for treatment of children with IgE-mediated CMA

3) To determine if successful OIT for children with CMA is associated with increases in blocking antibodies, including milk specific IgA and IgG4

4) To determine if successful OIT for children with CMA is associated with increases in Treg and/or Breg.

2.2 Rationale: CMA is a very common problem in children with important nutritional impact. Moreover, milk is among the most common foods associated with severe allergic reactions and anaphylaxis, and is extremely difficult to avoid. Treatment of CMA is currently based on strict avoidance, which is difficult to adhere to due to the ubiquitous nature of dietary dairy products. Treatment with oral immunotherapy (OIT) has been performed in the USA and Europe, but there are few rigorous, blinded clinical trials, with adequate controls and outcomes. However, there is no current research into OIT for CMA in Canada, depriving our population of a potential cure for this very common problem. A well defined clinical trial with adequate controls and immunological outcomes is essential for understanding the ideal patients and the safest and most efficacious methodologies, and for dissemination of successful milk specific OIT protocols to practitioners for more general use.

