3.3.4 Documentation: Subjects and families will be asked to complete daily home diaries to document that daily doses were taken, as well as to report accidental ingestions, problems with dose administration, or related symptoms. Follow-up visits in addition to or in conjunction with the weekly visits for dose escalation will be at 3, 6, 9, 12 months from completion of OIT. Each visit will include a medical history and physical examination, SPT, serum milk-specific IgE, IgA and IgG4 concentrations, Vitamin D levels, and B and T cell regulatory cell phenotyping will be measured at enrollment and at follow-up visits. (see Appendix C). Biweekly or monthly Telephone follow-up of these patients will be done prior to and following reaching the maximum tolerated dose. The telephone follow-up will review symptoms

and protocols for how to treat potential reactions.

3.3.5 Adverse reactions to OIT: All patients and their caregivers (if applicable) will be provided self-administered epinephrine, along with instructions and indications for administration and education about the nature of possible reactions to the desensitization therapy. Home diary forms will be provided to record the dose, date and time taken, symptoms occurring after the dose or any other time, and medications taken each day (Appendix D).

Safety measures: The patients' caregivers will be instructed **verbally and in writing** about the recommendations to be followed after desensitization and how to **treat** possible allergic reactions. They will also be given telephone and pager numbers of investigators and nurses for direct consultation 24/7. Parents will be instructed to contact the research team should any symptoms suggestive of an allergic reaction be present (appendix E, bottom of page).:

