4.0. Statistical Considerations

A: Sample Size calculation: Given that previous studies have attributed at least 50% improvement in the ability to tolerate milk(24) with an α of 0.05 and a power (1- β) of 0.80, a sample of 42 cases and 42 controls will be recruited.

B: Statistical Analysis: Statistical analyses will be performed using paired t-tests. A p value of <0.05 will be considered significant. Descriptive statistics of the variables including means, standard deviations and frequencies were computed for all study variables. The concentrations of milk –specific IgE, IgG and IgA, the size of the skin tests , T reg and Breg expression at the different study time-points will be compared with their baseline values using the one-sample paired t-test and to the control using a 2 sample t-test .

Multiple regression models will be used to assess factors associated with response to desensitization, including baseline demographic characteristics; gender; age; baseline SPT and specific IgE, Treg and Breg numbers, and vitamin D level.

5. Ethical Considerations

In the consent form given at study enrolment, participants will be advised that they will be randomly assigned to either oral immunotherapy or observation for a one year period. Participants will also be advised that their data will be shared only among the OIT study team. Participants in the observation control group who will not receive OIT treatment, will be told that they may to undergo such therapy after a year of observation and a positive oral food challenge.

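### Moderate and severe home reactions are counted without an exposure denominator, although the same reactions end dosing, so the mean count understates the reaction rate on therapy

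*Combined protocol and SAP*

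**What the plan says.** Section 2.1 makes safety the second objective: "To determine the safety of OIT for treatment of children with IgE-mediated CMA". Section 3.3.6 turns it into secondary outcome 1: "Number and severity of adverse reactions occurring after oral exposure to milk during the desensitization and follow-up phases". No unit of exposure is attached.

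Section 4.0 B assigns t-tests to antibodies, skin tests and regulatory cells, and regression to predictors of response. For reactions it names no method. Only the general sentence applies: "Descriptive statistics of the variables including means, standard deviations and frequencies were computed for all study variables".

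The paragraph on withdrawal from therapy (after section 3.3.5) removes children from treatment "if they have more than 2 or more moderate or severe reactions during the home (maintenance) OIT phase". A separate route covers the first two days: "Subjects will be withdrawn if they cannot tolerate the low dose, rush desensitization phase". The same paragraph says that "minor allergic reactions are common in these protocols (mild itching, abdominal discomfort) but resolve with increased time on therapy", and mild reactions are not part of the threshold. The protocol does not say whether withdrawn children stay in safety follow-up.

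Exposure is recorded. Section 3.3.5 states: "Home diary forms will be provided to record the dose, date and time taken, symptoms occurring after the dose or any other time". Daily use of medication goes into the same diary.

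**The concern.** Dosing stops because of the event being counted. A child prone to moderate or severe home reactions reaches the threshold early, takes fewer doses and adds no further reactions. A child who rarely reacts is exposed for the whole year. A mean count per child gives both equal weight and ignores the difference in exposure. The shortfall grows as such reactions become more frequent, so the summary is most flattering when the treatment is least safe.

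This matters because safety is a stated objective, and the rationale (section 2.2) wants to pass the regimen on to practitioners. They will want to know how often a child on treatment reacts.

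**Working it through.** The plan states no safety figure, so there is none to reproduce. The check asks how far a stop at the second or third reaction lowers the mean count.

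**Inputs.**
- From the protocol: the stop at the k-th moderate or severe home reaction. The wording allows k = 2 or k = 3.
- Assumed: the mean number m of such reactions per child had dosing continued, and how rates vary between children. The main case is gamma-Poisson with shape 1. Equal rates and shape 0.5 are sensitivity cases.

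**Formula.** With a stop at the k-th reaction, the observed count is min(N, k), so its mean is the sum of P(N ≥ j) for j = 1 to k. With shape 1, P(N ≥ j) = (m/(1+m))^j.

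- m = 0.5: 1/3 + 1/9 = 0.44 for k = 2; adding 1/27 gives 0.48 for k = 3.
- m = 2: 2/3 + 4/9 = 1.11; adding 8/27 gives 1.41.
- m = 3: 0.750 + 0.5625 = 1.31; adding 0.422 gives 1.73.

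Observed mean as a share of the uninterrupted mean:

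| True mean | Equal rates, k = 2 / 3 | Shape 1, k = 2 / 3 | Shape 0.5, k = 2 / 3 |
|---|---|---|---|
| 0.5 | 97% / 99% | 89% / 96% | 82% / 92% |
| 2 | 73% / 89% | 56% / 70% | 46% / 60% |

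At a true mean of 1 with equal rates the shares are 90% and 98%.

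**Does an exposure denominator repair it?** This was simulated with 200,000 children per scenario, shape 1 and a true mean of 2. In the second column, 70% of expected reactions fall in the first 16 of 52 weeks (an assumption), and the stop applies to all home dosing.

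| Summary (true value 2) | Constant rate, k = 2 / 3 | 70% early, k = 2 / 3 |
|---|---|---|
| Mean count | 1.11 / 1.41 | 1.11 / 1.41 |
| Total reactions ÷ total exposure | 1.46 / 1.62 | not run |
| One negative binomial model, exposure offset | 2.01 / 2.01 | 4.5 / 3.5 |
| Separate models for weeks 1–16 and 17–52, summed | not run | 1.7 / 1.8 |

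A single offset model is right only if each child's rate is constant. When reactions come early, withdrawn children contribute only high-rate time, and the model extrapolates it to the whole year. Separate models avoid that, but the later phase holds mainly children who react less, so its rate stays too low: 0.32 (k = 2) or 0.40 (k = 3) against a true 0.3 × 2 = 0.6.

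The proportion with at least one reaction is 2/3 in this example with or without the rule, because a stop at the second or third reaction cannot affect the first.

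**The case against.** Four arguments can be made for the plan.

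**The rule is narrow.** A reader might infer that it caps every child's total count. The documents do not support that. The threshold concerns moderate or severe reactions in the home phase, whereas the outcome covers all severities throughout desensitization and follow-up. If maintenance means only weeks 17–52 of Appendix B, escalation reactions do not count toward it either. This stands and limits the point. Part of the effect remains: mild home reactions also cease once dosing stops.

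**The plan has not chosen a biased estimator.** Reactions are graded (Appendix A), and frequencies could include the proportion of children affected. This partly stands. The plan is silent on the denominator. But following its text literally gives a mean count, with nothing to show the shortened exposure.

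**The count is correct for what happened.** It describes the burden under this protocol, withdrawal rule included, and that is a legitimate quantity. This stands, and is why the counts should be kept. It is not the rate while on treatment.

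**The loss may be small and the repair imperfect.** With rare reactions the loss is a few percent. A reader might also infer that an exposure offset recovers the truth. It does so only under a constant rate, whereas the protocol expects minor reactions to fade and the dose rises through week 16. In addition, once dairy is unrestricted after a tolerated 300 ml challenge (section 3.3.3), doses taken are no longer well defined. All of this stands and shapes the fix.

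**Conclusion.** The concern holds for moderate and severe home reactions, and for mild home reactions lost after withdrawal. Their mean count understates the rate on therapy, because the plan combines a count without a denominator, a summary limited to means, standard deviations and frequencies, and a stop triggered by the counted event.

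With shape 1, the understatement is 4 to 11% at a true mean of 0.5, 30 to 44% at 2 and 42 to 56% at 3. The lower figure in each pair is for a stop at the third reaction, the higher for a stop at the second. These sizes rest on assumed means and an assumed spread of rates. Appendix A grades cramping, vomiting and cough as moderate, so triggering events need not be rare, but no frequency is documented and a large bias cannot be asserted. The analysis should be changed because the direction is predictable and the data for a better summary are already planned.

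**What to change.** Keep the counts by severity and add the following to section 4.0 B.

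1. For all children randomized to OIT, report the proportions with at least one moderate or severe reaction, with epinephrine use, and with reaction-triggered withdrawal, each with an exact confidence interval.
2. Report reactions by severity per 100 diary-recorded doses, separately for the rush, escalation and maintenance phases, from phase-specific models with an exposure offset. Use child-time as the denominator once dairy is unrestricted.
3. Do not pool the phases in one constant-rate model. State that phase-specific rates reduce the bias from reaction-triggered withdrawal but do not remove it.
4. State whether safety follow-up continues after withdrawal.

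The sponsor should also reconcile the withdrawal wording. The phrase "if they have more than 2 or more moderate or severe reactions" can be read as the second or the third reaction, and it is unclear whether the home (maintenance) phase includes escalation doses taken at home. No threshold is proposed here.

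The cost is slightly more analysis, using diary data already planned. The safety picture may look less favourable than a mean count alone.
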